### Secondary outcomes

The secondary outcomes were the change in PaO2/FiO2 ratio, PaCO2 levels, and biventricular function before and after ICU transport. Pre-transport arterial blood gas (ABG) samples were obtained when the patient was ready to leave the operating room, and post-transport ABG samples were collected immediately upon arrival in the ICU. Left ventricular (LV) and right ventricular (RV) functions were visually assessed using VScan AIR SL (GE Medical, IL) transthoracic echocardiography (TTE) in the apical four-chamber and parasternal mid-papillary short-axis views before and after transport. Biventricular function was graded as moderate-to-severe hypokinesis (grade 1), mild hypokinesis (grade 2), normal (grade 3), or hyperkinesis (grade 4).

#### Point-of-care ultrasound (POCUS) training

Cardiac anesthesiologists received on-site training from a GE Healthcare representative on the assessment of biventricular function using the VScan Air ultrasound device.

#### Anesthesia and ventilation protocols

General anesthesia was induced via endotracheal intubation, and arterial, central venous, and pulmonary arterial lines were placed alongside the transesophageal echocardiography. The selection of anesthetic agents, inotropes, vasopressors, transfusion strategies, and fluid management was at the discretion of the attending anesthesiologist. Dexmedetomidine 0.7–1.0 mcg/kg/h was used for sedation during the transport to the ICU.

For manual ventilation, the AMBU bag technique, including the PEEP valve setting (5–10 cmH2O), was performed by each anesthesiologist. For mechanical ventilation using the Hamilton C1 ventilator, the respiratory therapist configured the ventilator to deliver a tidal volume and respiratory rate consistent with the final operating room settings (tidal volume: 6–8 mL/ideal body weight [kg], respiratory rate: 14–16 breaths/min, PEEP: 5–10 cmH2O, and FiO2:100%). Airway pressure and end-tidal CO2 levels were not monitored during transport.

#### Sample size determination and statistical analysis

Sample size calculations were based on prior clinical experience and data from a previous study. We hypothesized that 0% of patients receiving mechanical ventilation would experience a decrease in MAP during transport compared with 28% of those manually ventilated with an AMBU bag. With an alpha level of 0.05 and 90% power, we estimated that 38 patients per group (N = 76) would be required.

Summary statistics are presented for the demographic and clinical variables in each group. Continuous variables are expressed as mean  $\pm$  standard deviation (SD) or median (interquartile range [IQR]), as appropriate. Categorical data are summarized as frequencies

and percentages. Group comparisons were performed using the independent t-test or Mann–Whitney U test for continuous variables. Correlations between two continuous variables were assessed using Pearson's or Spearman's rank correlation test. Receiver operating characteristic (ROC) curve analysis was used to assess the accuracy of the predictive value of SVR for > 20% drop in MAP. Statistical significance was set at  $p < 0.05$ . All statistical analyses were performed using EZR (Saitama Medical Center, Jichi Medical University, Saitama, Japan), a graphical user interface for R (R Foundation for Statistical Computing, Vienna, Austria). More precisely, this is a modified version of R commander designed to add statistical functions that are frequently used in biostatistics.

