### Study participants

Patients aged > 18 years who underwent full sternotomy cardiac surgery and required postoperative ICU care were included in the study. The exclusion criteria included extubation in the operating room, postoperative need for mechanical circulatory support, postoperative open chest, and continuous inhalation of epoprostenol or nitric oxide.

For data analysis population, patients who needed to be switched the ventilation method from the originally designated method were excluded.

Eligible patients were randomized to either (1) manual ventilation using an AMBU bag (AMBU, Copenhagen, Denmark) or (2) mechanical ventilation using a Hamilton C1 ventilator (Hamilton Medical, Reno, NV) during transport to the ICU. Each participant provided verbal consent without knowing which arm they were assigned to. The anesthesiologist made the final decision regarding the ventilation modality based on the post-cardiopulmonary bypass biventricular function and PaO2/FiO2 or PaCO2 levels.

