### Primary outcomes

The primary outcomes included hemodynamic parameters before and after ICU transport. Hemodynamic indices mean arterial pressure (MAP). Pre-transport hemodynamic values were averaged from the final three readings (taken at 1-min intervals) before switching to the transport monitor, and post-transport readings were recorded immediately after transfer to the ICU monitor. Significant hypotension was defined as > 20% decrease in MAP between pre- and post-transport. The transport time began when the patient was switched to manual or mechanical ventilation and ended when the patient was switched to an ICU ventilator.

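### The continuous MAP, PaO2/FiO2 and PaCO2 comparisons carry no baseline covariate although each pre-transport value is collected; ANCOVA would generally be more precise for one degree of freedom per model

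*Combined protocol and SAP*

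**What the plan says.** The section Sample size determination and statistical analysis gives one rule for between-arm comparison of continuous variables: "Group comparisons were performed using the independent t-test or Mann–Whitney U test for continuous variables". ANCOVA, regression and baseline covariates appear nowhere in the document.

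The baselines are collected. Under Primary outcomes, "Pre-transport hemodynamic values were averaged from the final three readings (taken at 1-min intervals) before switching to the transport monitor"; the post-transport reading is taken once the patient is on the ICU monitor. Under Secondary outcomes, "Pre-transport arterial blood gas (ABG) samples were obtained when the patient was ready to leave the operating room", and a second sample follows on ICU arrival.

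The form of the outcome varies by section. For the blood gases, "The secondary outcomes were the change in" PaO2/FiO2 and PaCO2. MAP is described as a before-and-after measure, and the one explicit contrast for it is binary: "Significant hypotension was defined as > 20% decrease in MAP between pre- and post-transport". The analysis section does not say whether the t-test or Mann–Whitney test is applied to the change or to the post-transport value.

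**The concern.** A two-sample test of change assumes that post-transport values follow baseline with slope exactly 1. A two-sample test of the post-transport value assumes slope 0. ANCOVA estimates the slope from the data. Unless the true slope happens to be 0 or 1, the matching unadjusted test leaves explainable variation in the error term and does not properly remove a chance baseline difference between arms.

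Two things are at stake with 38 patients per arm. The intervals for continuous MAP and for the two blood-gas outcomes may be wider than the collected data require. And the two readings of the plan can give different estimates and different significance verdicts on the same data.

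**Working it through.** **The plan's own figure.** The plan assumes 0% against 28% with a MAP decrease, and "With an alpha level of 0.05 and 90% power, we estimated that 38 patients per group (N = 76) would be required". The two-sided pooled formula gives [1.960·√(2·0.14·0.86) + 1.282·√(0.28·0.72)]² / 0.28² = 30.1, so 31 per group. With continuity correction, (30.1/4)·[1 + √(1 + 4/(30.1·0.28))]² = 36.9, so 37. The stated 38 is therefore reproduced to within one patient. It sizes a binary comparison, and nothing below changes it.

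**Inputs.** The document gives 38 per arm (N = 76) and alpha 0.05, taken here as two-sided. It gives no SD and no pre/post correlation ρ for MAP, PaO2/FiO2 or PaCO2. The values of ρ (0.3, 0.5, 0.7), equal pre and post variances, normality, and a true difference of 0.6 SD are assumptions.

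**Gap between the two readings.** The post-only estimate minus the change-score estimate equals the difference in mean baseline. Its SD is √(2/38) = 0.229 baseline SD.

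**Variance of the arm difference**, in units of the post-only variance:
- post-only: 1
- change: 2(1 − ρ)
- ANCOVA: (1 − ρ²) × 73/72, where 73/72 = 1 + 1/(N − 4) is the cost of estimating one slope

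In large samples ANCOVA/change = (1 + ρ)/2 and ANCOVA/post-only = 1 − ρ². The 95% CI half-width is t × √(2/38 × variance), with 74 df for the unadjusted tests and 73 for ANCOVA. Power is from simulation, 40,000 trials per ρ.

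| | ρ = 0.3 | ρ = 0.5 | ρ = 0.7 |
|---|---|---|---|
| ANCOVA/change, large sample | 0.65 | 0.75 | 0.85 |
| ANCOVA/change, with 73/72 | 0.66 | 0.76 | 0.86 |
| ANCOVA/post-only, large sample | 0.91 | 0.75 | 0.51 |
| ANCOVA/post-only, with 73/72 | 0.92 | 0.76 | 0.52 |
| CI half-width, ANCOVA (SD) | 0.44 | 0.40 | 0.33 |
| CI half-width, change (SD) | 0.54 | 0.46 | 0.35 |
| CI half-width, post-only (SD) | 0.46 | 0.46 | 0.46 |
| Power at 0.6 SD, ANCOVA | 77% | 84% | 95% |
| Power at 0.6 SD, change | 59% | 73% | 92% |
| Power at 0.6 SD, post-only | 73% | 73% | 73% |

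Simulation error moves the power figures by up to about a point. At 0.6 SD the post-only and change tests reach different verdicts in 26% to 29% of simulated trials. All three tests hold type I error near 5%. With no true effect the two unadjusted verdicts still differ in about 8% of trials, and choosing between them after seeing both would give a false-positive rate of about 9%. Nothing in the document suggests that this was done.

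**Break-even, equal variances.** ANCOVA is worse than post-only only if ρ² < 1/73, that is ρ below about 0.12. It is worse than change only if (1 + ρ)/2 × 73/72 > 1, that is ρ above 144/73 − 1 = 0.97.

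**Unfavourable case for MAP.** Suppose true MAP carries over with slope 1, the SD of true change is 8 mmHg, the SD of a single reading is 5, and the true baseline SD is τ. All are assumed. Baseline is the mean of three readings and the post-transport value is taken as one.
- Change variance: 64 + 25/3 + 25 = 97.3
- Post variance: τ² + 89, which is 114 at τ = 5 and 189 at τ = 10
- ANCOVA residual variance: τ² + 89 − τ⁴/(τ² + 25/3), which is 89.0, 95.3 and 96.7 at τ = 0, 5 and 10

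Against change, ANCOVA variance is 9% to 1% lower before the 73/72 factor. After it, the range is 7% lower to 1% higher. Against post-only, after the factor, it is 0.85 at τ = 5 and 0.52 at τ = 10.

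**The case against.** The strongest reply is that the natural reading is already a test of change, certainly for the blood gases, so change is the fair comparator and the post-only figures describe an analysis few would run. Against change, the ratio (1 + ρ)/2 depends on equal variances as well as on ρ. Pre-transport MAP is a mean of three readings and no averaging is stated for the post-transport value, so equal variances are doubtful. In the slope-near-1 model, ρ is 25/√(33.3 × 114) = 0.41 at τ = 5, where the equal-variance formula with its small-sample factor gives 0.71 but the actual ratio is 0.99. At τ = 10, ρ is 0.70, and the figures are 0.86 and 1.007. This stands: the gain over change for MAP cannot be determined from the documents and may be nil. It does not remove the case for ANCOVA, whose worst outcome here is about 1% more variance.

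The trial is also sized on a binary contrast ("We hypothesized that 0% of patients receiving mechanical ventilation would experience a decrease in MAP during transport"), and the unadjusted tests are valid under randomization. Both are true, and both limit the point to efficiency and clarity.

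Finally, the anesthesiologist may override the modality on biventricular function or gas exchange, and "patients who needed to be switched the ventilation method from the originally designated method were excluded". Baseline differences in these variables may then be systematic. Every figure above assumes intact randomization and 38 analysed per arm. ANCOVA does not repair that selection.

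**Conclusion.** The point holds as a recommended improvement. The plan leaves collected baselines out of the model and does not name the tested quantity. Under equal variances and ρ from 0.3 to 0.7, adjustment saves 14% to 34% of the variance against change scores and 8% to 48% against post-only values, net of the estimated slope. In the slope-near-1 case for MAP the saving against change is negligible, with a downside of about 1%.

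Confidence is medium, because the correlations, variances and effect size are all assumed. The direction is safer than the size: across the cases examined ANCOVA is better than, or within about 1% of, the better unadjusted test, and it settles which quantity is analysed.

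**What to change.** In Sample size determination and statistical analysis, state that post-transport MAP, PaO2/FiO2 and PaCO2 are each analysed by ANCOVA with arm and the patient's own pre-transport value of the same variable, reporting the adjusted difference with its 95% CI. Keep the Mann–Whitney test on the change as a sensitivity analysis. If skewness is expected, as it may be for PaO2/FiO2, name the transformation or a robust alternative in advance.

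Leave the >20% MAP-drop comparison and the sample size outside this change. The section names no between-group test for proportions, but that is a separate matter.

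The cost is analysis wording and one degree of freedom per model, about 1.4% of variance at N = 76. No patients or measurements are added, and the named R-based software fits the model.

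### The between-arm comparison of MAP uses no baseline covariate, although pre-transport MAP is measured by protocol; this costs precision, not validity

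*Combined protocol and SAP*

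**What the plan says.** Under Primary outcomes, the Combined protocol and SAP states: "The primary outcomes included hemodynamic parameters before and after ICU transport". MAP is the index named. Its pre-transport value is the mean of three readings one minute apart, and its post-transport value is read on arrival at the ICU monitor. A fall of more than 20% is defined as significant hypotension.

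Under Sample size determination and statistical analysis, the method for comparing arms on continuous variables is: "Group comparisons were performed using the independent t-test or Mann–Whitney U test for continuous variables". The only other tools named are pairwise correlations and an ROC analysis of the "accuracy of the predictive value of SVR for > 20% drop in MAP". No regression, ANCOVA or stratification appears anywhere.

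SVR is mentioned only in that ROC sentence. Its time of measurement is not given, and it is not listed as a baseline variable or outcome. Under Anesthesia and ventilation protocols, "arterial, central venous, and pulmonary arterial lines were placed", so the means of deriving SVR in the operating room were in place. The text does not say that it was recorded.

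**The concern.** The plan holds one baseline value of the primary outcome, measured by protocol, and names a second variable that it suspects of predicting the outcome. Neither enters the randomised comparison. If either is related to MAP change, the part of the between-patient variance that it explains stays in the standard error. With 38 patients per arm, a chance difference between arms in that variable also moves the estimate in the trial actually run. Both effects have the same cause, the correlation between covariate and outcome, and should not be counted as two separate harms.

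At stake is the width of the confidence interval for the MAP difference, and a clear rule on adjustment fixed before the data are seen. Without such a rule, an observed baseline imbalance invites a choice between adjusted and unadjusted results after the fact.

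**Working it through.** **1. The plan's own sample size.** Inputs, all from the sample size paragraph: the error rates, "With an alpha level of 0.05 and 90% power"; the event rate in the ventilator arm, "We hypothesized that 0% of patients receiving mechanical ventilation would experience a decrease in MAP during transport"; an event rate of 28% in the manual arm; and the resulting size, "we estimated that 38 patients per group (N = 76) would be required". A two-sided test is assumed, because sidedness is not stated. With mean proportion 0.14:

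n0 = [1.96·√(2·0.14·0.86) + 1.282·√(0.28·0.72)]² / 0.28² = 30.1, rounded up to 31.

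With continuity correction: n = (n0/4)·[1 + √(1 + 4/(n0·0.28))]² = 36.9, rounded up to 37.

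This is within one patient of 38, so the figure reproduces. It concerns a binary event. No SD, no correlation and no target difference are given for continuous MAP.

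**2. Gain from one baseline covariate.** Assumptions: correlation r between the covariate and MAP change; a true difference of 0.5 SD of MAP change; 38 per arm; two-sided 5%. The comparator is an unadjusted t-test on MAP change. The plan does not say whether its test is applied to the change or to the post-transport value. In a linear model with pre-transport MAP as covariate, the arm coefficient is the same for either.

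Residual variance is multiplied by 1 − r², and the standardised difference becomes 0.5/√(1 − r²). Power comes from the t distribution with noncentrality equal to that difference times √(38/2).

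| r | Variance removed, r² | SE multiplied by | Equivalent extra patients, 1/(1 − r²) − 1 | Standardised difference | Power |
|---|---|---|---|---|---|
| 0 (unadjusted) | 0% | 1.00 | 0% | 0.500 | 58% |
| 0.3 | 9% | 0.95 | 10% | 0.524 | 62% |
| 0.4 | 16% | 0.92 | 19% | 0.546 | 65% |
| 0.5 | 25% | 0.87 | 33% | 0.577 | 70% |

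Using one or two fewer of the 74 degrees of freedom changes these powers by less than 0.1 percentage point.

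**3. What SVR adds to pre-transport MAP.** SVR is calculated partly from MAP, so the two probably overlap. For illustration, assume that pre-transport MAP correlates 0.4 with MAP change and 0.5 with SVR, and that SVR correlates r with MAP change, all in the same direction. Then

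R² = (0.4² + r² − 2·0.4·r·0.5) / (1 − 0.5²).

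- r = 0.3: R² = 0.13/0.75 = 0.173, power 66%
- r = 0.4: R² = 0.16/0.75 = 0.213, power 68%
- r = 0.5: R² = 0.21/0.75 = 0.280, power 72%

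Pre-transport MAP alone gives 65%, so SVR adds about 1, 3 or 7 points. Used alone against no adjustment, it would add 4, 7 or 12. Other correlations or signs would change this.

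**4. Chance imbalance.** The standard error of the arm difference in a covariate is √(2/38) = 0.23 SD, and its 95% limit is 1.96·0.23 = 0.45 SD. At r = 0.4, that limit moves the unadjusted MAP difference by 0.4·0.45 = 0.18 SD. If the imbalance happens to be two standard errors, the conditional type I error of the unadjusted test is

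1 − Φ[(1.96 − 2r)/√(1 − r²)] + Φ[(−1.96 − 2r)/√(1 − r²)],

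which is about 8%, 10% or 13% at r = 0.3, 0.4 or 0.5.

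**5. On average over randomisations.** In simulations without a true effect (4,000 trials each at r = 0.3 and 0.5), the t-test rejected in 5.1% and 4.5%. The unadjusted test therefore keeps its nominal level.

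**The case against.** The strongest reply is that nothing is broken. Under randomisation the unadjusted test is unbiased on average and its standard error already allows for chance imbalance. The 0.18 SD shift is an extreme at an assumed correlation, not an expected error. All of this stands.

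Second, the 0.5 SD scenario is not the plan's. On a normal model with a common SD, event rates of 5% against 28% correspond to a difference of 1.06 SD, and 1% against 28% to 1.74 SD. Power then exceeds 99% without adjustment. For the binary contrast actually hypothesised, 38 per group gives 97.4% by Fisher's exact test. If the effect is as large as hypothesised, adjustment adds almost nothing to power. It would still narrow the interval for any covariate that predicts the outcome, and it matters for power if the true effect is smaller.

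Third, a reader might infer that SVR is an established predictor, already recorded before transport, and that leaving it out distorts the result. The documents do not support this. An ROC analysis asks whether SVR predicts; it does not show that it does. The time of measurement is not stated. If SVR were read during or after transport, adjusting for it would condition on a variable that ventilation may have affected, and could itself introduce bias.

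Finally, baseline adjustment does not address the provisions under Study participants that the anesthesiologist makes the final decision on modality and that switched patients are excluded from analysis. Those are separate matters, and the statement that the unadjusted test is valid assumes intact random allocation.

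What survives is narrower: pre-transport MAP is unquestionably a baseline value of the primary outcome, and the plan does not use it.

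**Conclusion.** The point holds as a matter of efficiency. The planned MAP comparison uses no baseline covariate, and pre-transport MAP is the clear omission. SVR is a possible second covariate, conditional on a pre-transport reading. The loss is precision and sensitivity to chance imbalance in the trial at hand. It is neither average bias nor an inflated overall type I error.

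The size cannot be settled from the documents. At a correlation of 0.3 or less, the standard error falls by about 5% or less. At 0.5 it falls by about 13%, equivalent to one third more patients. The power figures also rest on an assumed 0.5 SD difference, and SVR's own contribution may be only a few points.

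**What to change.** Specify the MAP comparison as a linear model of post-transport MAP on arm with pre-transport MAP as covariate. Report the adjusted arm difference with its 95% confidence interval, and keep the unadjusted test as a supporting analysis.

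State how and when SVR is measured. Add it as a second covariate only if it is defined and recorded before transport; otherwise leave it out of the arm comparison.

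For the fall of more than 20%, a risk difference standardised over the covariates from a Firth-penalised logistic model can be added, but as support only. Zero events are hypothesised in the ventilator arm, so ordinary logistic regression would face separation.

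The cost is a change of wording and one or two of 74 degrees of freedom. Pre-transport MAP needs no new data; whether SVR does depends on what was recorded. If the covariates turn out to predict nothing, almost nothing is lost.

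### Does the ROC analysis of SVR need a stated reading time, SVR formula, patient set and confidence interval before it can be used?

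*Combined protocol and SAP*

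**What the plan says.** Under *Sample size determination and statistical analysis*, the ROC analysis is described in full by: "Receiver operating characteristic (ROC) curve analysis was used to assess the accuracy of the predictive value of SVR for > 20% drop in MAP". This is the only mention of SVR in the document. It is not listed under *Primary outcomes* or *Secondary outcomes*, and MAP is the only hemodynamic index that the primary outcome section names.

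Four other places bear on how the sentence would be carried out:

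- **Event.** *Primary outcomes*: "Significant hypotension was defined as > 20% decrease in MAP between pre- and post-transport".
- **Timing of readings.** *Primary outcomes*: "Pre-transport hemodynamic values were averaged from the final three readings (taken at 1-min intervals) before switching to the transport monitor". The second set of values is taken as soon as the ICU monitor is in use.
- **Means of obtaining SVR.** *Anesthesia and ventilation protocols*: "arterial, central venous, and pulmonary arterial lines were placed alongside the transesophageal echocardiography". No cardiac output method is named.
- **Patients.** *Study participants* sets one analysis population for the trial, which leaves out anyone whose ventilation method had to be changed from the one assigned. It says nothing specific to the ROC analysis.

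The statistics section sets a significance level of 0.05 and mentions no confidence interval for the AUC or for any other estimate.

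**The concern.** Three things are left unwritten, and each could in principle change what the AUC means.

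- **Reading time.** SVR is conventionally calculated as (MAP − CVP) / cardiac output × 80. Hemodynamic readings are taken both before and after transport. If the post-transport SVR were used, its numerator would hold the post-transport MAP that decides whether the patient counts as an event. The AUC would then partly restate the outcome.
- **Patients.** A curve on all patients and a curve on the manual arm answer different questions. If events occur only under manual ventilation, as the planning hypothesis may imply, no curve can be estimated in the ventilator arm.
- **Precision.** With few events, an AUC given without an interval could be read as firmer than it is.

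This is also the only planned analysis that names the >20% drop, since tests between groups are given for continuous variables only: "Group comparisons were performed using the independent t-test or Mann–Whitney U test for continuous variables". A reader may therefore give it more weight than a supporting analysis usually gets.

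**Working it through.** **1. The plan's own figure.** Inputs from the sample size paragraph: 28% versus 0%, alpha 0.05, power 90%, 38 per group. Two-sided, without correction:

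n = [1.960·√(2 × 0.14 × 0.86) + 1.2816·√(0.28 × 0.72)]² / 0.28² = (0.962 + 0.575)² / 0.0784 ≈ 30.1, so 31.

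With the continuity correction: (30.1/4) × [1 + √(1 + 4/(30.1 × 0.28))]² ≈ 36.9, so 37. The stated 38 is reproduced to within one patient per group and is not in question. The plan gives no figure for the ROC analysis.

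**2. Expected events.** The hypothesis reads "We hypothesized that 0% of patients receiving mechanical ventilation would experience a decrease in MAP during transport compared with 28% of those manually ventilated". It speaks of a decrease, not of a >20% decrease, so applying the rates to the ROC event is an assumption. On that assumption, with nobody excluded, 0.28 × 38 = 10.6, or about 11 events, all in the manual arm. The binomial 2.5th to 97.5th percentile range is 5 to 16.

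**3. Precision of the AUC.** Hanley–McNeil: SE² = [A(1−A) + (n₁−1)(Q₁−A²) + (n₀−1)(Q₂−A²)] / (n₁n₀), with Q₁ = A/(2−A) and Q₂ = 2A²/(1+A). At an assumed A = 0.75, Q₁ = 0.6000, Q₂ = 0.6429 and A² = 0.5625.

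Manual arm, 11 events and 27 non-events: (0.1875 + 10 × 0.0375 + 26 × 0.0804) / 297 = 0.00893, so SE = 0.0945.

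| Events vs non-events | SE | 95% half-width |
|---|---|---|
| 11 vs 27 (manual arm) | 0.0945 | 0.185 |
| 11 vs 65 (both arms) | 0.0893 | 0.175 |
| 5 vs 33 (manual arm) | 0.1328 | 0.260 |
| 16 vs 22 (manual arm) | 0.0832 | 0.163 |

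At 11 vs 27, an observed AUC below about 0.70 has an interval that reaches 0.5. The number of events drives the width, and the choice of patient set barely alters it.

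**4. Pooled or manual arm.** Assume SVR has the same distribution in both arms and all events are in the manual arm. A ventilator-arm patient is then a 28/72 mix of event-like and non-event-like SVR, so the AUC of events against that arm is 0.28 × 0.5 + 0.72A. Weighting 0.72 × 38 = 27.36 manual non-events and 38 ventilator patients:

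pooled AUC = [27.36A + 38(0.14 + 0.72A)] / 65.36.

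Manual-arm values of 0.70, 0.75, 0.80 and 0.85 become 0.667, 0.709, 0.751 and 0.793. The differences are 0.03 to 0.06, well inside the half-widths at 11 events.

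**5. Reading time.** The size of the feared artefact can be simulated with SVR given no true predictive effect, low SVR as the marker and 200,000 patients per scenario. Every input is assumed: MAP mean 75, between-patient SD 6 to 12, pre-transport noise SD 4 or 5, post-transport variation SD 8 or 10, mean change of −5 or tuned to 28% events, cardiac output 5 (SD 1.2), CVP 10 (SD 3).

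- Pre-transport SVR: AUC 0.46 to 0.55.
- Post-transport SVR, cardiac output unchanged: 0.73 to 0.79.
- Post-transport SVR, about half the MAP change through cardiac output: 0.63 to 0.71.
- Post-transport SVR, all of the change through cardiac output: 0.51 to 0.60.

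Within a scenario the post-transport AUC exceeds the pre-transport one by about 0.05 to 0.31. That gap arises only if the post-transport reading is used. The pre-transport reading shares the pre-transport MAP with the event definition, yet its AUC stays near 0.5 in these scenarios.

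**6. What the text supports.** A value recorded after the fall cannot predict it. The ROC sentence speaks of predictive value, and the averaging rule under *Primary outcomes* covers pre-transport hemodynamic values in general, a class to which SVR belongs. Nothing points to a post-transport SVR. The ROC sentence names no arm, so the ordinary reading is everyone in the general analysis population.

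**The case for a change.** The strongest case for a change is that implication is not specification. The averaging rule is not tied to SVR, the monitoring lines do not by themselves give a formula or a cardiac output method, and the general analysis population does not say whether the arms are pooled. An uninformative SVR could look moderately predictive from an unstated choice of reading alone, and a few sentences would close the gap without new data.

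The omissions are real, and the arithmetic holds. But the large shift needs an analyst to read *predictive* against its meaning, and its upper end also needs cardiac output to stay constant. It measures a hypothetical misreading, not a result the plan leads to. On patients, either set is defensible, and the difference is smaller than the sampling error. The missing interval runs through the whole plan and is not particular to this analysis. Reporting one would show the imprecision but not reduce it. A label of exploratory would add little for a variable that is neither a primary nor a secondary outcome.

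**Conclusion.** No change to the plan is called for. This is missing detail in a supporting analysis, and an analyst following the document would fill it sensibly: pre-transport SVR, everyone in the stated analysis population, and preferably an interval beside the AUC. The randomised comparison and the sample size are untouched.

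The imprecision is worth remembering when the result is read: about ±0.18 at an AUC of 0.75 with 11 events, and from ±0.16 to ±0.26 in the manual arm over 16 down to 5 events. This rests on taking 28% and 0% as rates of a >20% drop, on 38 analysed patients per arm, and on a hypothetical AUC. The 0.03 to 0.06 effect of pooling further assumes similar SVR distributions in the two arms. The shift of 0.05 to 0.31 applies only if a post-transport SVR were used, and under assumed variances that the document does not give. If a published AUC turned out to rest on the post-transport reading, that would be a criticism of how the analysis was carried out.

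### The ROC analysis tests SVR alone for a >20% fall in MAP, so it cannot show whether SVR adds anything to pre-transport MAP, which enters both SVR and the event (minor)

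*Combined protocol and SAP*

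**What the plan says.** The section on sample size and statistical analysis contains one prediction analysis: "Receiver operating characteristic (ROC) curve analysis was used to assess the accuracy of the predictive value of SVR for > 20% drop in MAP". SVR is the only predictor named.

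The event comes from the section on primary outcomes: "Significant hypotension was defined as > 20% decrease in MAP between pre- and post-transport". The baseline is measured as follows: "Pre-transport hemodynamic values were averaged from the final three readings (taken at 1-min intervals) before switching to the transport monitor". For the second value, "post-transport readings were recorded immediately after transfer to the ICU monitor"; no averaging is mentioned there.

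SVR appears nowhere else. The document gives no formula and no measurement time for it, does not list it as an outcome, and does not say whether high or low SVR is expected to predict a fall. The anesthesia section is consistent with the usual calculation, since "arterial, central venous, and pulmonary arterial lines were placed alongside the transesophageal echocardiography". No analysis compares SVR with pre-transport MAP or with cardiac output, and no model contains both SVR and MAP.

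**The concern.** If SVR is calculated in the usual way from pre-transport values, one quantity, pre-transport MAP, sits on both sides of the analysis. A patient whose MAP is temporarily high before transport has a higher calculated SVR. Through regression to the mean, the same patient may also be more likely to show a fall of more than 20%. An ROC curve of SVR alone cannot separate this from information that SVR carries beyond MAP.

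What is at stake is the reading of a supporting result. An AUC above 0.5 could be reported as evidence for SVR, which needs a cardiac output measurement, when the pre-transport blood pressure already on the monitor might discriminate as well or better.

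**Working it through.** **Inputs from the document.** Event: (pre − post)/pre > 0.20. Planned rates: "We hypothesized that 0% of patients receiving mechanical ventilation would experience a decrease in MAP during transport compared with 28"% of those ventilated by hand. I take these as rates of the >20% fall. Size: "we estimated that 38 patients per group (N = 76) would be required".

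**The plan's own figure.** No AUC or ROC sample size is stated, so the only figure to reproduce is 38 per group ("With an alpha level of 0.05 and 90% power"; two-sided assumed).
- Mean rate: 0.14.
- Uncorrected: n = [1.96·√(2·0.14·0.86) + 1.2816·√(0.28·0.72)]² / 0.28² = (0.962 + 0.575)² / 0.0784 ≈ 30.1, so 31.
- Continuity-corrected: (30.1/4)·[1 + √(1 + 4/(30.1·0.28))]² ≈ 36.9, so 37.

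The stated 38 is reproduced to within one patient. Expected events: 0.28 × 38 + 0 × 38 = 10.6, about 11 of 76.

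**Assumed inputs (not in the document).**
- SVR = 80 × (MAP − CVP)/CO, measured before transport.
- Pre MAP mean 78, SD 8–12, with the same SD after transport.
- CO mean 5 (SD 1.0–1.5) and CVP mean 10 (SD 3), both independent of MAP and of the fall.
- Event rate 14% or 28%.

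**Mechanism.** Take CVP 10 and CO 5. At MAP 78, SVR = 80 × 68/5 = 1088; at MAP 88 it is 80 × 78/5 = 1248. The event threshold is 0.8 × 78 = 62.4 in the first case and 0.8 × 88 = 70.4 in the second, a rise of 8. With pre–post correlation ρ and equal SDs, the expected post MAP rises by 10ρ: 3 at ρ = 0.3, 5 at 0.5, 7 at 0.7, 8 at 0.8 and 9 at 0.9. Below 0.8 the threshold rises faster than the expected post MAP, so high MAP (and high SVR) goes with more events. At 0.8 the two cancel, and above it the direction reverses. Formally, the event is 0.8·pre − post > 0, and Cov(pre, 0.8·pre − post) = σ²(0.8 − ρ).

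**Size.** Simulation of 200,000 patients per scenario, with the post mean set to give the event rate and the AUC computed by ranks:

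| Pre–post correlation | AUC of SVR | AUC of pre-transport MAP |
|---|---|---|
| 0.3 | 0.58–0.65 | 0.72–0.74 |
| 0.5 | 0.56–0.61 | 0.65–0.67 |
| 0.7 | 0.52–0.55 | 0.56–0.57 |
| 0.8 | about 0.50 | about 0.50 |
| 0.9 | 0.42–0.46 | 0.38–0.39 |

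Cardiac output alone gives 0.50 throughout, so in this set-up all of SVR's discrimination comes from MAP.

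**Against sampling error.** Hanley–McNeil at AUC 0.5 with 11 events and 65 non-events: variance = [0.25 + 10 × 0.0833 + 64 × 0.0833]/(11 × 65) = 6.417/715 = 0.00897, so SE ≈ 0.095. Within the 0.3–0.7 range, the departure from 0.5 runs from 0.02/0.095 ≈ 0.2 to 0.15/0.095 ≈ 1.6 standard errors.

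**The case against.** **The effect needs cardiac output not to track MAP.** A reader might infer that SVR would discriminate even if vascular tone carried no information. The document does not support that. By the formula, a high MAP at an unrelated cardiac output is a high calculated resistance, so the set-up above lets resistance move with MAP. When tone is made independent of MAP and cardiac output follows from MAP and tone, the AUC of SVR is 0.497–0.502. When cardiac output instead follows the patient's underlying MAP level and misses the fluctuation in the pre-transport reading, SVR departs from 0.5 again (0.59–0.70), and at a correlation of 0.7 it sometimes exceeds MAP alone (for example 0.660 against 0.610). Nothing in the document shows which case applies. This objection stands, and it limits the point to whether SVR adds to MAP.

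**Sign and size rest on an unknown correlation.** The two readings bracket one transport and the first is a mean of three, which favours a higher correlation and a smaller effect. Averaging over a few minutes does not remove slower fluctuation, however, and vasopressors and fluids are discretionary. If the fractional change is unrelated to pre-transport MAP, the effect vanishes (AUC 0.499 in simulation). This stands as a limit on size.

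**Small numbers matter more.** By normal approximation, true AUCs of 0.55, 0.60 and 0.65 would be declared significantly above 0.5 about 8%, 18% and 35% of the time. This is true, but more patients would reduce the noise and leave the shared component in place.

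**SVR is undefined and no direction is given.** If low SVR were the hypothesis, the shared component would work against it at correlations below 0.8. If SVR were measured after transport, a separate simulation gives AUCs of 0.25–0.37, the opposite direction. Defining SVR therefore comes first, but a definition alone does not remove the overlap.

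**A marker can be useful without being incremental.** This is fair. Making any SVR claim depend on a two-term logistic model with about 11 events (5–6 per term) would be too strict.

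**Conclusion.** The point holds as a minor one. As planned, the analysis cannot distinguish discrimination by SVR from discrimination by the pre-transport MAP inside it. Under the stated assumptions the shared component alone moves the AUC of SVR to about 0.52–0.65 at correlations of 0.7 down to 0.3, to about 0.50 at 0.8, and below 0.5 at 0.9. In that set-up pre-transport MAP discriminates more strongly than SVR except near 0.8, where neither does.

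This rests on the standard SVR formula, a pre-transport value, cardiac output and CVP unrelated to MAP and to the fall, and equal SDs. None of these is in the document. It does not show that an SVR finding would be spurious, or that bias in favour of SVR is inevitable. The randomised comparison, the primary outcome and the sample size are not touched.

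**What to change.** In the statistical analysis section:

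- State that SVR is the pre-transport value, and give its formula and the time at which its components are read.
- Report the AUCs of pre-transport MAP and of cardiac output beside that of SVR, each with a confidence interval, and compare SVR with MAP by a paired DeLong test.
- Describe SVR as a marker beyond blood pressure only if that comparison supports it. Otherwise report its AUC as descriptive.
- Label any logistic model containing both MAP and SVR as exploratory.

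The cost is a few lines of text and a little extra analysis. It needs no new patients and, if SVR is calculated in the usual way, no new measurements, because MAP and cardiac output are its components. The drawbacks are that the comparisons will be imprecise with about 11 events and that the SVR claim may come out weaker.
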